9. STATISTICAL METHODS

This is a randomized, parallel group, non-comparative phase II trial evaluating the safety and efficacy of two schedules of fixed-dose pembrolizumab combined with standard cisplatin-IMRT in intermediate or high risk, PULA HNSCC: sequential and concurrent. This study is being performed in order to provide: a) necessary safety experience; b) preliminary efficacy estimates; c) characterization of the PD-L1 biomarker in the context of definitive chemoradiation; d) the recommended schedule for definitive testing.

Primary Objective

To evaluate two schedules of fixed-dose pembrolizumab (concurrent vs. sequential) added to standard, concurrent cisplatin-IMRT in patients with PULA HNSCC, in order to recommend the schedule to be tested in a subsequent definitive, randomized study.

Sample Size Determination

The target sample size is 40 evaluable patients per arm. Assuming 10% drop out or ineligibility, 90 patients will be randomized (all evaluable patients will be analyzed). The sample size is determined based upon the following assumptions: 1) the 1-year PFS in the high risk population treated with conventional cisplatin-radiotherapy is 60%;⁶ 2) As defined, DLTs occurring in more than 20% of the study population are unacceptable and would constitute an unsafe regimen; 3) The study requires adequate power to detect a signal of antagonism, defined as a 1-year local failure rate

[figure not shown]
exceeding 60%. To advance to Phase II/III testing, a treatment arm must meet all of the following criteria:

- DLT occurs in $\leq 20\%$
- 1-year local failure rate is $< 60\%$
- 1-year PFS is $\geq 60\%$

If both arms meet the above criteria, then the treatment arm demonstrating numerically superior 1-year PFS will advance for definitive testing, as in a so-called “pick-the-winner” trial model. An early phase trial cannot provide the statistical power required for a formal statistical comparison between arms.

The graphic in Figure 1 below demonstrates the probability of accepting either treatment (that is, based on $n = 40$ evaluable patients per arm) by means of 90% one-sided exact confidence intervals (CI) for DLT, 1-year failure rate, and 1-year PFS. If the upper bound of the DLT CI is less than 0.20, the upper bound of the failure CI is less than 0.60, and the lower bound of the 1-year PFS CI is greater than 0.60, the treatment will be accepted.

Figure 1: Probability of accepting the treatment according to the three primary metrics

Early Stopping Rule

Dose Limiting Toxicity (DLT; see Section 5.8 for DLT definition) will be continuously monitored in both treatment arms, and is explicitly intended for the purposes of safety monitoring of the concurrent combination of pembrolizumab and cisplatin-IMRT (Arm 2). As defined, excess DLT is not expected during standard of care cisplatin-IMRT. Excess DLT in either arm, however, would trigger the early stopping rule. A continuous Bayesian stopping rule will be adopted, once 4 patients have accrued to either treatment arm. For either arm, if $p(p(DLT) > 0.2) \geq 0.6$, then the stopping rule would be triggered. Table 11 describes the number of DLTs per number of treated patients required to trigger the early stopping rule, which will require a suspension of accrual to that Arm and evaluation of toxicity data by the H&N Program DSMC to determine further action.

Table 11. Boundaries for the Early Stopping Rule for Excess DLT

	Number of patients treated on that Arm
--	--

	4	8	12	16	20	24	28	32	36
Accrual to the arm is halted if the number of DLTs is greater than or equal to	2	3	4	4	5	6	7	8	9

Analysis Plan

The proportions of patients experiencing DLT, local failure at 1 year, or are progression-free at one year will be calculated with exact (Klopper-Pearson) 90% confidence intervals. Adverse events will be tabulated by category and grade. The relationship between the three primary metrics and baseline PD-L1 expression will be assessed using logistic regression.

Secondary Endpoints

Toxicity

All patients will be evaluable for toxicity from the time of their first treatment with pembrolizumab. The proportion of DLTs in each dosing arm (concurrent vs. sequential) will be reported, as will the proportion of AEs in accordance with NCI CTCAE v.4 grading criteria.

Preliminary efficacy data

Overall and progression-free survival in both arms will be characterized by product-limit (Kaplan-Meier) survival function estimates with appropriate confidence intervals. The study is not adequately powered for a formal test comparing PFS between arms.

10. LABELING, PACKAGING, STORAGE AND RETURN OF CLINICAL SUPPLIES 10.1Investigational Product

The investigator shall take responsibility for and shall take all steps to maintain appropriate records and ensure appropriate supply, storage, handling, distribution and usage of the investigational product, pembrolizumab, in accordance with the protocol and any applicable laws and regulations.

Clinical Supplies will be provided by Merck

as summarized in Table 7. Table 12. Product

Descriptions

Product Name & Potency	Dosage Form
Pembrolizumab 50 mg	Lyophilized Powder for Injection
Pembrolizumab 100 mg/ 4mL	Solution for Injection

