6.1.3.7 Time to Progression and Progression-free survival

This interval will be measured from the date of entry on the study to the appearance of new metastatic lesions or objective tumor progression. Progression-free survival (PFS) will be calculated from treatment initiation to disease progression or death from any cause or last follow up.

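### The 1-year PFS and local-failure gates rest on an efficacy set that is never defined, have no rule for unknown 1-year status, and are stated in two forms that disagree

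*Combined protocol and SAP*

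**What the plan says.** Section 9, Sample Size Determination, targets 40 evaluable patients per arm: "Assuming 10% drop out or ineligibility, 90 patients will be randomized (all evaluable patients will be analyzed".

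The acceptance rule is given twice in that subsection.
- **Point form.** "To advance to Phase II/III testing, a treatment arm must meet all of the following criteria": DLT in at most 20%, 1-year local failure below 60%, 1-year PFS of at least 60%.
- **Bound form.** One-sided 90% exact intervals are used, and for PFS the condition reads "the lower bound of the 1-year PFS CI is greater than 0.60, the treatment will be accepted".

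If both arms qualify, "then the treatment arm demonstrating numerically superior 1-year PFS will advance for definitive testing".

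The Analysis Plan says that the proportions with DLT, "local failure at 1 year, or are progression-free at one year will be calculated with exact (Klopper-Pearson) 90% confidence intervals", without repeating that the interval is one-sided. Evaluability is defined only under Toxicity: "All patients will be evaluable for toxicity from the time of their first treatment with pembrolizumab". Kaplan-Meier appears only among the secondary endpoints: "Overall and progression-free survival in both arms will be characterized by product-limit (Kaplan-Meier) survival function estimates".

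Section 6.1.3.7 says that PFS "will be calculated from treatment initiation to disease progression or death from any cause or last follow up". Local failure has no definition anywhere in the document.

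**The concern.** The gates and the ranking decide which schedule goes forward, but the denominator for two of the three metrics is open. The planned allowance for drop-out sits outside the 40 per arm, so a patient lost before one year may be left out, counted as a failure or counted as a success. The trial is open-label, so a rule chosen late would be chosen with outcomes in view.

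If the toxicity set were borrowed for efficacy, the arms would be treated differently. Section 5 starts pembrolizumab at week 9 in Arm 1 and week -1 in Arm 2. An Arm 1 patient who progresses or leaves during chemoradiotherapy would fall out of the denominator, while a similar Arm 2 patient would stay in. That could tilt the choice between arms.

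The two forms of the gate are a further gap: the same result can pass one and fail the other.

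**Working it through.** **Sample size (Section 9).** 40 / (1 - 0.10) = 44.4, so 45 per arm and 90 in total. The stated figure reproduces, assuming equal allocation, since no ratio is stated.

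**The two gates at n = 40.** Point form for PFS: 0.60 x 40 = 24 or more. Bound form: the one-sided 90% Clopper-Pearson lower limit is the 0.10 quantile of Beta(x, n - x + 1).

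| Progression-free | Lower limit | Point form | Bound form |
|---|---|---|---|
| 24/40 | 0.486 | pass | fail |
| 28/40 | 0.588 | pass | fail |
| 29/40 | 0.615 | pass | pass |

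So 24 to 28 of 40 passes one form and fails the other. At a true 60%, P(Bin(40, 0.6) >= 24) = 0.568 and P(Bin(40, 0.6) >= 29) = 0.071. If the Analysis Plan's interval is two-sided 90%, 29/40 has limit 0.586 and fails; 30/40 has 0.613 and passes.

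For local failure, the upper limit is 0.588 at 19/40 (pass) and 0.612 at 20/40 (fail). The point form allows up to 23/40 (57.5%), so 20 to 23 is in dispute.

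**One unknown patient.** Under the one-sided bound, with 39 known, the unknown decides the gate when exactly 28 are progression-free: P(Bin(39, p) = 28).

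| True PFS | 60% | 65% | 70% | 75% | 80% |
|---|---|---|---|---|---|
| Bound form | 4.3% | 9.3% | 13.7% | 12.7% | 6.6% |

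Under the point form the critical count is 23, and the probability is 12.8% at a true 60% and 0.1% at 80%. For local failure under the bound, P(Bin(39, q) = 19) is 6.9% at 40%, 12.5% at 50% and 0.6% at 30%.

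**Handling rule.** Assumptions: 45 eligible patients, exponential PFS, each lost with probability 10% at a uniform time in year 1 independently of outcome, one-sided 90% bound (log-log Greenwood for Kaplan-Meier).

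| Rule | Pass at true 60% | Pass at true 75% |
|---|---|---|
| Drop only those lost event-free | 5.0% | 66.6% |
| Exclude all drop-outs | 7.2% | 71.8% |
| Kaplan-Meier | 9.0% | 77.7% |

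Only the first rule is biased (58.6% on average at a true 60%). Kaplan-Meier gains over full exclusion because it uses 45 rather than about 40 patients. With 43 eligible and 5% loss, the figures at 75% are 69.9%, 72.2% and 76.1%. If the whole 10% is ineligibility, the gain is nil. In selection at 70% versus 80%, the better arm leads in 85% to 86% of trials under every rule.

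**When status is read.** IMRT lasts 7 weeks (Section 5.4.1), and scans follow at 9 and 12 months after radiotherapy, within one month (Section 8.4). From treatment start in Arm 1 these fall at 7 + 39 = week 46 and 7 + 52 = week 59, and one week later in Arm 2. Without radiotherapy delay, neither window covers week 52. A Kaplan-Meier estimate at exactly week 52 therefore sees scan-detected events only up to the 9-month scan. Simulating the 45-patient case at a true 60%, with scans at weeks 20, 33, 46 and 59, the false-pass rate is about 9% if events are seen when they occur, about 13% if half are found only on scans, and about 19% if all are. A crude week-52 proportion shares the bias.

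**The case against.** A binary 1-year endpoint with exact intervals is legitimate and matches the 40-patient design. One sentence classifying unknowns would close that gap without Kaplan-Meier, and excluding all drop-outs is unbiased when loss is unrelated to outcome. Sections 5.5 and 8.4 continue follow-up for progression and survival, so unknowns should be few. Any threshold has a patient who can tip it. The scan argument is also fragile: Arm 2's 9-month window ends at week 51.5, so a one-week radiotherapy delay would cover week 52, and Section 5.4.12 contemplates breaks of up to ten treatment days.

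Most of this stands. It makes Kaplan-Meier the better choice rather than the only one, and it limits how often the missing rule will matter. It does not supply a denominator, a classification of unknowns, or a choice between the two gates.

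A reader might infer that the plan uses the toxicity set for efficacy and so favours Arm 1. The documents do not say that; the tilt arises only if that definition is borrowed. A reader might also infer that the crude proportion would often pick the wrong schedule. The selection figures do not support that. Nor is the sample size wrong: 90 reproduces.

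**Conclusion.** The concern holds for three gaps in Section 9: no efficacy analysis set, no rule for unknown 1-year status, and two acceptance rules that disagree. The last is the largest in size and needs no assumption about loss: at a true 60% and 40 patients, the PFS criterion is passed 57% or 7% of the time depending on which form governs. The effect of one unknown, 4% to 14% under the one-sided bound, is conditional on an unknown occurring. The Kaplan-Meier gain, about 78% against 72% at a true 75%, rests on an assumed 10% loss among 45 eligible patients. The plan does not split its 10% between drop-out and ineligibility, and the gain shrinks or vanishes if it is mostly ineligibility. Changing the estimator does not by itself cure the scan-timing bias.

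**What to change.** 1. State which form of the gate governs, and that its bound is one-sided 90%.
2. For PFS and the selection step, analyse all eligible randomized patients by assigned arm, with eligibility judged on baseline data only. Keep the pembrolizumab-treated set for DLT only.
3. Use the 1-year Kaplan-Meier estimate, already planned as secondary, with a one-sided 90% bound. Show best-case and worst-case handling of unknown status as sensitivity analyses. If the exact proportion is kept, fix the classification of unknowns in advance.
4. Fix one time origin and name the scan that settles 1-year status in both arms, and apply the estimate at that assessment rather than at exactly week 52.
5. Define local failure as a first-failure endpoint, with distant progression and death without local failure as competing events. Section 8.4 lets patients stop scheduled assessments after any documented progression, so later local failures may go unseen. Without this rule, more neck imaging would be needed.

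**Cost.** New SAP wording and a rerun of Figure 1. The bound is no longer exact. If lost patients fail at twice the hazard (an assumption), the false-pass rate at a true 60% is 11.6% by Kaplan-Meier, above the nominal 10%, against 12.2% if drop-outs are excluded. The PFS origin in Section 6.1.3.7 changes if randomization is chosen.

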6.1.2.1.3 Progressive Disease (PD)

At least a 20% increase in the sum of target lesion diameters (longest diameter of the primary tumor; short axis diameter of the target lymph nodes), taking as reference the *smallest sum diameter* recorded since the baseline sum diameter measurements, or the appearance of one or more new lesion(s).

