6.1.2.1.4 Stable Disease (SD)

Neither sufficient shrinkage to qualify for PR nor sufficient increase to qualify for PD.

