8.4 Long Term Follow Up

After the end of treatment visit, patients will be evaluated every 3 months for 21 months (+/- 2 weeks), then every 6 months (+/- 1 month) for one year, then annually (+/- 1 month) for two years, which will represent a total of 5 years from completion of IMRT. Thus, long-term follow-up evaluations will start approximately 6 months after completion of IMRT, and will include the following:

- History and physical examination and performance status.
- Vitals signs, including weight.
- Assessment for late toxicity, including dysphagia, xerostomia, gastrostomy tube dependence, pain, fibrosis and lymphedema within the head and neck, hypothyroidism, late autoimmune events.
- Thyroid function testing (TSH, FT4).
- Complete blood count, including platelets and differential.
- Blood chemistries (may be obtained from whole blood or serum/plasma sample), including BUN, creatinine, electrolytes (K+, Na+, Cl-, CO2), calcium, Mg++ and liver function tests (bilirubin, AST (SGOT), ALT (SGPT), and alkaline phosphatase, total protein, albumin)
- During the long term follow-up period, tumor assessments will be performed 6, 9, 12, 18, 24, 36, 48, and 60 months after completion of radiotherapy (+/- one month). The minimum protocol imaging requirement is: contrasted, diagnostic neck and chest CT at intervals specified above. More intensive imaging may be conducted per local practice.
- Swallowing assessments per local practice and as indicated by post-radiotherapy evaluation and patient-reported symptoms.
- Note: patients who have documented progression may discontinue scheduled study assessments and will be followed only for survival. Survival assessments will be performed every 6 months (+/- 2 months) by telephone contact and/or by evaluation of the Social Security Death Index or other public records.

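### Does the missing definition of 1-year local failure leave the go/no-go decision open?

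*Combined protocol and SAP*

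**What the plan says.** Under Sample Size Determination, section 9 requires an arm to meet all of three criteria: DLT in at most 20%, 1-year local failure below 60%, and 1-year PFS of at least 60%. The reason for the second is "The study requires adequate power to detect a signal of antagonism, defined as a 1-year local failure rate" exceeding 60%. The same section also states the rule through one-sided 90% exact bounds at 40 evaluable patients per arm: "the upper bound of the failure CI is less than 0.60, and the lower bound of the 1-year PFS CI is greater than 0.60". The Analysis Plan treats all three as simple proportions: "The proportions of patients experiencing DLT, local failure at 1 year, or are progression-free at one year will be calculated" with exact 90% intervals.

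Section 6 defines response, progression, PFS and survival, but not local failure. Progression in target lesions needs "At least a 20% increase in the sum of target lesion diameters" or a new lesion, and stable disease is "Neither sufficient shrinkage to qualify for PR nor sufficient increase to qualify for PD". Section 8.3.3 adds that residual disease found at consolidation surgery within 24 weeks of IMRT is not a progression event.

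On timing, "Progression-free survival (PFS) will be calculated from treatment initiation to disease progression or death from any cause or last follow up" (section 6.1.3.7), while "tumor assessments will be performed 6, 9, 12, 18, 24, 36, 48, and 60 months after completion of radiotherapy" (section 8.4). Section 8.4 also says that "patients who have documented progression may discontinue scheduled study assessments and will be followed only for survival".

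**The concern.** A metric that can veto an arm should leave no doubt about what is counted. Three things are unwritten.

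- **Persistent disease.** A patient whose local tumour shrinks partly or stays the same size is a partial responder or stable, so not a PFS event. A reader interested in antagonism might still call that patient a local failure.
- **The clock.** PFS starts at treatment initiation and scans are timed from the end of radiotherapy, so it is not obvious which scan closes the year.
- **Other first events.** Patients who die or progress elsewhere first may have no later local assessment.

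If these choices could turn the same data from go to no-go, they would be open to influence once results were visible, because the trial is open-label (section 14.3).

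**Working it through.** **Inputs from section 9.** 40 evaluable patients per arm; 10% dropout; thresholds 0.60 for local failure and 0.60 for PFS; one-sided 90% exact bounds. The planned number reproduces: 40/0.90 = 44.4, rounded up to 45 per arm, 90 in all. The power display for the three metrics (Figure 1) is not shown in the supplied text, so it cannot be checked.

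**Cut-offs at n = 40 (Clopper-Pearson, one-sided 90%).**
- PFS: 29/40 has lower bound 0.615 (pass) and 28/40 has 0.588 (fail). A pass allows at most 40 − 29 = 11 PFS events.
- Local failure: 19/40 has upper bound 0.588 (pass) and 20/40 has 0.612 (fail).
- Point rule: PFS of at least 60% allows at most 40 − 24 = 16 events. Local failure fails from 24/40.
- Antagonism aim: with true local failure of 60%, the criterion alone rejects with probability P(X ≥ 20) = 0.926.

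**Reading A: every local failure is also a PFS event on the same clock.** Local failures cannot exceed PFS events. A PFS pass caps local failure at 11/40 = 27.5% (upper bound 0.385), or at 16/40 = 40% on the point rule. Neither reaches 20 or 24, so the probability of passing PFS and failing local failure is 0.

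**Reading B: persistent, non-progressing disease also counts.** In an arm that only just passes PFS with every event local, the criterion needs a further 20 − 11 = 9 of 29 progression-free patients (31%) with such disease, or 24 − 16 = 8 of 24 (33%) on the point rule.

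For probabilities, let p be true 1-year PFS, s the share of PFS events that are local, and r the share of progression-free patients with persistent disease. Then

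P(decision changes) = Σₑ P[Bin(40, 1−p) = e] · Σₗ P[Bin(e, s) = l] · P[Bin(40−e, r) ≥ L − l],

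with e up to 11 and L = 20 (bound rule), or e up to 16 and L = 24 (point rule). The values of p, s and r are assumptions. Results at p = 80%:

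| Rule, local share | r = 10% | r = 20% | r = 30% | r = 40% |
|---|---|---|---|---|
| Bound, 100% | 0.02% | 2.36% | 20.86% | 57.71% |
| Bound, 70% | <0.01% | 0.34% | 6.37% | 31.46% |
| Point, 100% | <0.01% | 0.15% | 2.99% | 19.58% |
| Point, 70% | <0.01% | 0.01% | 0.39% | 5.28% |

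Other values of p move these figures. With all events local, the bound rule at p = 75% gives 3.05% (r = 20%) and 22.06% (r = 30%). The point rule at p = 70% gives 12.15% (r = 30%). In the most extreme cell above, the true local-failure rate on Reading B is 0.20 + 0.80 × 0.40 = 52%, close to the level the criterion is meant to catch.

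**Clock.** IMRT ends 7 weeks (Arm 1) or 8 weeks (Arm 2) after treatment starts. The 9-month scan falls at about week 46 or 47 and the 12-month scan at about week 59 or 60. Suppose the hazard is constant and events are dated at scans. Reading local failure at the later scan then adds about 1.8 events of 40 (PFS 80%) to 3.1 (PFS 60%). At least 9 would be needed to turn a bare PFS pass on the bound rule. The change in decisions is below 0.1%.

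**Death or distant progression first.** In an arm with 11 PFS events, the harshest handling calls all of them local: 11/40, which passes. Dropping d such patients gives (11 − d)/(40 − d), which is never above 11/40. No handling changes a decision.

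**The case for a change.** The strongest opposing case is that the protocol itself creates a group with local tumour that is not a PFS event, and that failure to clear local tumour is a natural form of antagonism. If the sponsor meant that group to count, an analyst who leaves it out could advance an arm that the sponsor would have stopped. One sentence would settle it, and response and pathology are already recorded.

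The first part stands: the definition is absent, and two analysts could differ. The consequence is weaker. It needs a rate of persistent disease that the documents do not give, and the large percentages need 30 to 40% together with a high local share. The text also leans towards Reading A. Section 8.3.3 keeps residual disease at early consolidation out of progression, and section 1.1 pairs local with distant failure, as components of failure by site. That is inference, not a definition.

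Nor is there an obviously better rule to write in. Counting only proven residual disease would tie the metric to biopsies and neck dissections that sections 8.3.1 and 8.3.3 leave to the surgeon. Counting imaging findings would rest on post-radiation CT, whose specificity section 6.2.4 considers inadequate.

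Sections 5.6 and 8.3.3 do differ on whether the exemption for residual disease has a time limit, and they must be reconciled. Section 5.6 concerns stopping treatment, and the treatment period falls mostly inside the 24 weeks, so this is a cross-reference matter.

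**Conclusion.** No change to the plan follows. This is a definition left unwritten that analysts would fill sensibly by taking local failure as local progression on the PFS clock. On that reading the criterion changes no decision at n = 40, under either form of the rule, and protection against antagonism comes through PFS. Alone, the local-failure criterion still rejects a true 60% rate with probability 0.93 on the bound rule. It does not rank the arms either: if both qualify, section 9 chooses on numerical 1-year PFS.

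The clock and the handling of other first events affect the reported rate, not the decision. The residual uncertainty is confined to the reading that counts persistent disease. At true PFS 80% it is at most 2.4% of decisions (bound) or 0.15% (point) with 20% of progression-free patients affected, and at most 20.9% or 3.0% with 30%. These figures rest on assumed rates and local shares, and on independent binomial counts. A documented persistent-disease rate of about 30% or more would make the wording matter; nothing supplied shows one.

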2.2 Secondary

Secondary objectives for this study include:

- To evaluate the toxicity of two sequences of the combination of pembrolizumab and concurrent cisplatin-IMRT in patients with PULA HNSCC.

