5. TREATMENT PLAN

Arm 1 (Table 2): Pembrolizumab will be initiated 2 weeks after the completion of cisplatin-IMRT (week 9 of protocol treatment) and administered at the fixed dose of 200 mg IV q 3 weeks (+/- 3 days) for a total of 24 weeks (8 doses; 6 months). NOTE: Per discretion of the treating investigator, the week 9 dose of pembrolizumab may be delayed up to 3 weeks for recovery of acute toxicities from chemoradiotherapy. This dose would be considered delayed, and all subsequent doses would be administered at a q 3 week interval (+/- 3 days) from first pembrolizumab dose.

Arm 2 (Table 3): Pembrolizumab will be initiated 1 week prior to cisplatin-IMRT (the “window”) at the dose of 200 mg IV q 3 weeks (+/- 3 days). Pembrolizumab will be continued concurrently through cisplatin-IMRT (weeks 3, 6), and continued for a 15 week maintenance period after completion of cisplatin-IMRT for a total pembrolizumab treatment period of 24 weeks (8 doses; 6 months). NOTE: Per discretion of the treating investigator, the week 9 dose of pembrolizumab may be delayed up to 3 weeks for recovery of acute toxicities from chemoradiotherapy. This dose would be considered delayed, and all subsequent doses would be administered at a q 3 week interval (+/- 3 days) until completion.

Table 2. Arm 1 Treatment Plan

ARM 1	Week of Treatment														
	1	2	3	4	5	6	7	9	12	15	18	21	24	25	30
IMRT	X	X	X	X	X	X	X								
Cisplatin	X	X	X	X	X	X	X								
Pembrolizumab								X	X	X	X	X	X	X	X

Table 3. Arm 2 Treatment Plan

ARM 2	Week of Treatment													
	-1	1	2	3	4	5	6	7	9	12	15	18	21	
IMRT		X	X	X	X	X	X	X						
Cisplatin		X	X	X	X	X	X	X						
Pembrolizumab	X			X			X		X	X	X	X	X	

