5.2.3 Dosing Schedule

Patients will receive cisplatin once weekly as an IV infusion over 60 minutes, for a total of 7 doses.

Cisplatin should be administered on Monday, Tuesday, or Wednesday of each treatment week and may be given either before or after the radiation therapy fraction that is given on the same day. When cisplatin and pembrolizumab are administered on the same day, pembrolizumab should follow cisplatin.

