5.4 Intensity Modulated Radiotherapy (IMRT)

5.4.1 Dose specifications

IMRT will be delivered in 35 fractions over 7 weeks (five fractions per non-holiday week) in one plan (SIB). Concomitant boost using separate IMRT plans is not allowed.

Missed treatments due to holidays or logistic reasons can be compensated for by delivering an additional BID treatment during the week, OR treating on the Saturday or Sunday of that week, OR adding to the end of treatment.

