5.4.13 Radiation Therapy Adverse Events

The descriptions and grading scales found in the revised NCI Common Terminology Criteria for Adverse Events (CTCAE), version 4 will be utilized for grading all adverse events. All appropriate treatment areas should have access to a copy of the CTCAE, v. 4. A copy of the CTCAE, v. 4 can be downloaded from the CTEP web site (<http://ctep.cancer.gov>).

Grade 3 therapy-induced mucositis and/or dysphagia are expected to develop in about one third to one half of patients. Nutritional evaluation prior to the initiation of therapy for a prophylactic gastrostomy (PEG) tube placement is highly recommended. Placement of a feeding tube should be recorded on the appropriate case report form, as should use of a feeding tube during and after treatment (e.g., greater than or less than 50% of nutrition by tube). Other common radiation adverse events include: fatigue, weight loss, regional alopecia, loss of teeth or cavities, xerostomia, hoarseness, transient ear discomfort, dysgeusia, increased sensitivity of the skin to hot and cold temperature as well as the sun and skin erythema and desquamation within the treatment fields.

Less common long-term treatment adverse events include: hypothyroidism, loss of hearing, chronic swallowing dysfunction requiring permanent feeding tube, brachial plexopathy, and cervical fibrosis. Much less common radiation adverse events include: mandibular osteoradionecrosis (< 5% incidence with attention to dental recommendations), and cervical myelopathy (< 1% with restriction of spinal cord dose to ≤ 45 Gy).

Rare but serious side effects that may develop including fibrotic tissue formation, soft tissue ulceration and/or irritation or damage to the skin within the neck that may result in bleeding. Blindness and the development of secondary (new) cancers and tumors is very rare but also possible.

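### Toxicity is evaluable only from the first pembrolizumab dose, so adverse-event proportions include the chemoradiation weeks in Arm 2 but not in Arm 1

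*Combined protocol and SAP*

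**What the plan says.** Section 2.2 has a single bullet: "To evaluate the toxicity of two sequences of the combination of pembrolizumab and concurrent cisplatin-IMRT in patients with PULA HNSCC". The object of study is therefore the whole sequence, chemoradiation included.

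Section 9, under Secondary Endpoints, Toxicity, sets the start of observation: "All patients will be evaluable for toxicity from the time of their first treatment with pembrolizumab". The next sentence says what is reported on that basis: "The proportion of DLTs in each dosing arm (concurrent vs. sequential) will be reported, as will the proportion of AEs", graded by CTCAE version 4.

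Section 5 gives the two start dates. For Arm 1, "Pembrolizumab will be initiated 2 weeks after the completion of cisplatin-IMRT (week 9 of protocol treatment"; a delay of up to three weeks is allowed so that acute chemoradiation toxicity can settle. For Arm 2, "Pembrolizumab will be initiated 1 week prior to cisplatin-IMRT".

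The backbone is the same in both arms: "IMRT will be delivered in 35 fractions over 7 weeks" (Section 5.4.1) and "Patients will receive cisplatin once weekly as an IV infusion over 60 minutes, for a total of 7 doses" (Section 5.2.3).

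**The concern.** One event, the first pembrolizumab dose, opens the toxicity clock in both arms, but it falls on opposite sides of the most toxic part of the regimen. A grade 3 mucositis in week 5 counts in Arm 2. The same event in week 5 of Arm 1 precedes evaluability.

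The rule also selects patients. Section 5.4.12 takes patients off study when treatment interruptions exceed three weeks. An Arm 1 patient lost in this way during chemoradiation never receives pembrolizumab and never enters the toxicity set. The corresponding Arm 2 patient has been in it since week -1.

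At stake is the descriptive toxicity account of each schedule. Section 9 says the study is meant to supply safety experience and a recommended schedule. Two schedules with identical true toxicity would be reported with a higher AE rate for the concurrent one, and Arm 1's rate would leave out seven weeks of its own treatment.

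**Working it through.** **Inputs.** First pembrolizumab dose: week 9 in Arm 1 (week 12 at the latest if delayed by the full three weeks) and week -1 in Arm 2 (Section 5, Tables 2 and 3). Chemoradiation: weeks 1 to 7, with 7 cisplatin doses and 35 fractions. Evaluable patients: 40 per arm (Section 9). Expected acute toxicity: "Grade 3 therapy-induced mucositis and/or dysphagia are expected to develop in about one third to one half of patients" (Section 5.4.13).

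**Plan's own figure.** 40 / 0.9 = 44.4, rounded up to 45 per arm; 2 × 45 = 90 randomised, as stated. Nothing below changes it.

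**Step 1: chemoradiation inside the evaluable period.** Count the weeks from 1 to 7 that fall on or after the first pembrolizumab dose, at 7 × 5 = 35 fractions in all.

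| | Arm 1 | Arm 2 |
|---|---|---|
| First pembrolizumab | week 9 | week -1 |
| Chemoradiation weeks counted | 0 of 7 | 7 of 7 |
| Cisplatin doses counted | 0 of 7 | 7 of 7 |
| Fractions counted | 0 of 35 | 35 of 35 |

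Section 5.3.1 places the first post-chemoradiation dose in week 10, not week 9. The two sections should be reconciled, but the count is the same under either.

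**Step 2: size of the artefact.** Let r be the true proportion with grade 3 mucositis/dysphagia, equal in both arms. Let f be the fraction of Arm 1 cases still present at week 9 and counted. The documents give no value for f, and do not say whether an event that began before the first dose and is still ongoing counts. Arm 2 reports r and Arm 1 reports r × f, so the gap is r × (1 − f).

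| f (assumed) | r = 1/3 | r = 1/2 |
|---|---|---|
| 0 | 33.3 points | 50.0 points |
| 0.25 | 25.0 points | 37.5 points |
| 0.5 | 16.7 points | 25.0 points |

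In patients, Arm 2 would report 40 × 1/3 = 13.3 to 40 × 1/2 = 20 cases. The Clopper-Pearson 90% intervals are 20% to 47% for 13/40 and 36% to 64% for 20/40. With f = 0, Arm 1 would report 0/40, interval 0% to 7%, which overlaps neither.

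**Step 3: the same count under a common start.** From the first dose of any protocol treatment (week 1 in Arm 1, week -1 in Arm 2), both arms have 7 of 7 chemoradiation weeks, and the gap is zero when r is equal.

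**Step 4: the DLT denominator under a common start.** Section 5.7.1 requires a DLT to be at least possibly related to pembrolizumab and to occur within 24 weeks of starting it, so a patient who never starts cannot have one. Suppose 5 of 45 Arm 1 patients never start and 9 of the other 40 have a DLT. The proportion is 9/40 = 22.5% among those treated with pembrolizumab and 9/45 = 20.0% among all treated. The first fails and the second meets Section 9's listed criterion of at most 20%. The fix must not move this denominator.

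**The case against.** The strongest reply is that the plan does not discard the Arm 1 data. Section 8.2.1 requires weekly toxicity assessment with attribution in Arm 1 during weeks 1 to 7. Section 11.1 has all AEs recorded whatever the study group. The Analysis Plan in Section 9 also promises an AE tabulation without naming a start date. On this view the evaluability sentence is really about DLT, which it directly precedes and which is counted from pembrolizumab start in both arms.

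Much of this stands. Collection is complete, and for DLT the sentence is coherent. But collecting events does not define the analysis period. The same paragraph reports AE proportions as well as DLT, and a tabulation with no stated window does not override the only start that is stated. If the sponsor means every AE to count, the text still has to say so.

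It also stands that the trial is declared non-comparative, so no between-arm AE test is invalidated. Zero persistence is an extreme as well: the permitted delay of the week 9 dose shows that the protocol expects some acute toxicity to remain then.

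A reader might infer that the secondary objective cannot be answered at all. The documents do not support that, because the missing weeks are already recorded and need only be admitted to the analysis. Nor is toxicity the only secondary endpoint: Section 9 lists preliminary efficacy under the same heading.

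**Conclusion.** The stated rule gives the wrong result for AE proportions. It observes Arm 2 through all seven chemoradiation weeks and Arm 1 through none, and it removes Arm 1 patients who never reach pembrolizumab. The per-arm proportions are not comparable even descriptively, and Arm 1's does not measure the sequence in Section 2.2.

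For grade 3 mucositis/dysphagia the artefact is at most about 33 to 50 points, falling to about 17 to 25 points if half the Arm 1 cases persist and are counted. This rests on the literal reading of the rule, equal true rates in both arms, the protocol's own one third to one half, and an assumed persistence fraction.

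A reader might also infer that the choice of schedule is compromised. The documents do not support this. An arm advances on DLT, 1-year local failure and 1-year PFS, with numerically better 1-year PFS deciding if both arms qualify; AE proportions play no part. The DLT stopping rule is likewise untouched, since the DLT definition carries its own window from pembrolizumab start in both arms.

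**What to change.** Replace the evaluability sentence with two rules.

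- *AE proportions:* every patient who receives any protocol treatment is evaluable from the first dose of any protocol treatment (week 1 in Arm 1, week -1 in Arm 2). AEs are tabulated by arm for the whole course, and separately for the chemoradiation phase and the post-chemoradiation phase.
- *DLT proportion:* the existing window from pembrolizumab start is kept, and the denominator is restricted to patients who received pembrolizumab.

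The cost is a short text change and one extra split of the AE table. No new data, visits or patients are needed. The small downside is that Arm 1's reported AE rates become less favourable.
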